2.3 Study Rationale

This study will investigate AZD0466 in patients with advanced haematological malignancies for which there are limited treatment options, including patients with intermediate and higher risk MDS. Patients with intermediate and higher risk MDS who are on a clinical continuum with AML have equally very poor prognosis and may also receive benefit from AZD0466 ([Estey et al 2022](#), [Greenberg et al 2012](#), [Vardiman et al 2009](#)).

The study is modular in design; the core protocol will contain study information applicable to all patients in this study. Module 1 will evaluate the safety, tolerability, PK, and efficacy of AZD0466 as monotherapy. Module 2 is a DDI study that will evaluate AZD0466 with voriconazole, a strong inhibitor of CYP3A4. The mechanism of action and nonclinical in vivo data suggest the potential to combine AZD0466 with a number of other anticancer treatments, resulting in enhanced activity. Further modules may be added via protocol amendment, where permissible by local regulations, and will include AZD0466 in combination with other anticancer treatments.

3 OBJECTIVES AND ENDPOINTS - CORE

The objectives and endpoints that are common to all study modules are shown in [Table 2](#). See

individual modules for the objectives and endpoints specific for each of the modules.

Table 2 Objectives and Endpoints

Objectives	Endpoints/Variables
Primary	

 To assess the safety and tolerability of AZD0466 in patients with advanced haematological malignancies 	
 Incidence of AEs and SAEs Changes from baseline in laboratory findings, physical examinations, performance status, electrocardiograms, and vital signs
Secondary	

 To characterise the PK profile of AZD0466 following intravenous administration (via PK profiles of the active moiety AZD4320 in plasma) 	
 Plasma concentrations and derived PK parameters for total and released AZD4320
Exploratory	

 CCl 	
 CCl

 CCl 	
 CCl

 CCl 	
 CCl

 CCl 	
 CCl CCl

AE, adverse event; CCl ; SAE, severe adverse event.
	

; PK, pharmacokinetics; CCl ;
	

4 STUDY DESIGN - CORE

4.1 Overall Design

This is a modular Phase I/II, open-label, multi-centre study in patients with advanced haematological malignancies with limited treatment options. Each module will evaluate the safety, tolerability, PK, and preliminary efficacy of AZD0466 as monotherapy or in combination with other treatments in the patient population. The initial protocol includes 2 modules; additional modules may be incorporated via regulatory amendments to the protocol together with any additional documents (eg, updates to quality and/or nonclinical information). Up to 4 additional modules may be added, where permissible by local regulations. The structure of this study protocol is shown in [Figure 2](#); the core protocol contains elements common to all modules, and the individual modules contain the module-specific details relevant to that module.

Figure 2 Modular Protocol Design

Core Clinical Study Protocol		

• Synopsis• Study background, rationale and benefit-risk assessment• Core objectives and endpoints• Study population• Core inclusion and exclusion criteria• Concomitant medication and lifestyle restrictions• Dose modifications• Discontinuation of study treatment and participant withdrawal• End of study		
Module 1 AZD0466 monotherapy	Module 2 AZD0466-voriconazole interaction	Additional Modules

• Module background, rationale and benefit-risk assessment• Schedule of activities• Specific objectives and endpoints• Module study design• Specific inclusion and exclusion criteria• Study treatment, dose escalation• Module assessments• Statistical considerations	
• Module background, rationale and benefit-risk assessment• Schedule of activities• Specific objectives and endpoints• Module study design• Specific inclusion and exclusion criteria• Study treatment• Module assessments• Statistical considerations	

As the mechanism of action of AZD0466 and in vivo data suggest that combining AZD0466 with other anticancer treatments may result in enhanced activity, it is anticipated that the study may evolve to incorporate additional modules to allow further evaluation of AZD0466 in defined populations or novel combinations. Emerging data from Module 1 (AZD0466 monotherapy) will guide the development of further modules to evaluate AZD0466 in novel combinations or defined patient populations, and findings from Module 2 will guide the use of concomitant medications in patients with advanced haematological malignancies. Hence, the modular study design will allow tailoring of study procedures and endpoints to specific treatment regimens and indications. The rationale for each module will be described in the respective module.

This study will characterise the PK profile of AZD0466 following intravenous (IV) administration (via PK profiles of the active moiety AZD4320 in plasma). Plasma concentrations and derived PK parameters for total and released AZD4320 will be determined and specified in each module.

As part of the clinical drug development program for AZD0466, AstraZeneca will investigate **CCI**

CCI profiles and their relationship to drug effect. There are many potential benefits of this exploratory research, including identification of patients most likely to benefit from treatment, those who may not respond to treatment; and those who may experience adverse reactions. Ultimately, this research will provide the information and understanding required to deliver well tolerated and effective new medicines to patients.

4.2 Rationale for Study Design

The rationale for each module will be described in the respective modules.

4.2.1 Regulatory Amendments for Additional Modules

Additional modules will be provided as regulatory amendments to the protocol together with any additional documents (eg, updates to quality and/or nonclinical information, etc.) to the clinical trial application as required. Up to 4 additional modules may be added, where permissible by local regulations.

4.3 Justification for Dose

Refer to individual modules for details.

4.4 End of Study Definition

The end of the study is defined as the date of the last visit of the last patient in the study or last scheduled procedure shown in the Schedule of Activities (SoA) for the last patient in the study globally.

The End of Module is defined as the date of the last visit of the last patient in a Module or the last scheduled procedure shown in the respective SoA for the last patient in that Module.

A patient is considered to have completed the study if he/she has completed all phases of the study module including the last visit or the last scheduled procedure shown in the SoA including follow-up for overall survival (OS).

Patients may be withdrawn from the study if the study itself is stopped. The study may be stopped if, in the judgement of AstraZeneca, study patients are placed at undue risk because of clinically significant findings. The study may be terminated at individual centres if the study procedures are not being performed according to ICH GCP or if the recruitment rate does not

allow for completion of the study in the planned timeframe.

The results from each Module will be reported to regulatory authorities in accordance with clinical trial regulatory maintenance requirements in each region.

Following attainment of the final analyses for all modules and the overall end of study milestone, a final Clinical Study Report (CSR) including individual module reports and an assessment of fulfilment of the core clinical trial objectives will be produced for submission to Regulatory Authorities by the required timelines (ie, within 1 year of the overall end of the study).

4.5 Criteria for Stopping or Pausing Study Recruitment

AstraZeneca reserves the right to pause recruitment, temporarily suspend, or permanently terminate this study or components of the study at any time. AstraZeneca may at any point during the study pause enrolment if at least one of the following occurs:

- Fatal event deemed related to study intervention by the Sponsor and in discussion with the SRC after full aetiological work-up. This will also result in a comprehensive review of safety.
- Unexpected and life-threatening events deemed related to study treatment by the Sponsor and in discussion with the SRC.
- Sponsor decision that study patients are placed at undue safety risk (also see Section 4.4).
- Sponsor decision to discontinue the development of the study treatment in the proposed indications.

During Part A of Module 1 and during Module 2, AstraZeneca pharmacovigilance process and the SRC will evaluate toxicities study-wide (including evaluation of previous doses).

During Part B of Module 1, AZD0466 monotherapy dose expansion, a safety analysis will be performed at the time of the first interim analysis (IA) in each cohort. The study recruitment may be paused, pending investigation by the Sponsor and in discussion with SRC, if > 30% of patients experience AEs leading to study treatment discontinuation (see Section 11.7.9), the SRC may decide to stop the study, modify the study, or continue the study, based on the overall risk benefit of the agent. In addition, individual cohort level stopping criteria are provided in Section 11.7.2.2. Throughout the expansions, the AstraZeneca safety team and the SRC, will regularly review cumulative safety data including, but not limited to, toxicities that meet the DLT criteria.

5 STUDY POPULATION - CORE

Prospective approval of protocol deviations to recruitment and enrolment criteria, also known as protocol waivers or exemptions, is not permitted.

Each patient must meet all of the inclusion criteria and none of the exclusion criteria for this study at the time of starting study treatment. Under no circumstances can there be exceptions to this rule.

5.1 Core Inclusion Criteria

The inclusion criteria that are applicable to all modules in the study are described in this section. Additional module-specific criteria are included in the specific modules. If specific module criteria are more stringent than the core inclusion criteria, the module criteria must be met.

Informed Consent

- 1 Provision of signed and dated written informed consent prior to any study-specific procedures, sampling, and analyses. Informed consent is described in Appendix [A 3](#), which includes compliance with the requirements and restrictions listed in the informed consent form (ICF) and in this protocol.
 - If a patient declines to participate in optional exploratory research and/or genetic component of the study, there will be no penalty or loss of benefit to the patient and he/she will not be excluded from other aspects of the study.

Age

- 2 Patient must be aged \geq 18 years, at the time of signing the informed consent. In some countries parental consent may be required in addition to an assent form for patients who are 18 years of age.

Patient and Disease Characteristics

- 3 Diagnosis of AML, ALL, or intermediate or higher risk myelodysplastic syndrome (MDS; Part A only), which is histologically proven based on criteria established by the World Health Organization (WHO) as documented by medical records.
- 4 Patients must have received at least one prior line of therapy, and an established standard of care with proven benefit, and for which the patient is eligible, must not be available at the time of enrolment.
- 5 For AML or ALL patients, documented active disease requiring treatment that is relapsed or refractory defined as:
 - Recurrence/relapse of disease after response to prior line(s) of therapy
 - Progressive disease (refractory) on/after completion of the treatment regimen preceding entry into the study

- 6 For intermediate and higher risk MDS, documented active disease is defined as:
 - Patients with > 10% blasts, and/or
 - MDS with intermediate, high, or very high risk (risk score > 3) per the Revised International Prognosis Scoring System (IPSS-R) ([Appendix O](#)).
- 7 Eastern Cooperative Oncology Group (ECOG) performance status ≤ 2 . Performance status must not have deteriorated by ≥ 2 levels within 2 weeks after providing informed consent.
- 8 Predicted life expectancy ≥ 8 weeks.
- 9 White blood cell count must be $< 10 \times 10^9/L$ prior to the first dose in Cycle 1, Day 1. Treatment with hydroxyurea (AML) or high-dose steroids (ALL and leukaemia of ambiguous lineage) during screening and Cycle 1 to control white blood cell count is permitted. Both medications can be started or stopped at any point during this period.
- 10 Adequate organ function at screening defined in [Table 3](#):

Table 3 Organ Function Parameters

Category	Parameter	Value
Hepatic	Total bilirubin	$\leq 1.5 \times \text{ULN}$
		$\leq 3 \times \text{ULN}$ in presence of Gilbert's syndrome
	AST and ALT	$\leq 2.5 \times \text{ULN}$
Coagulation	INR	$< 1.5 \times \text{ULN}$
Pancreatic	Lipase	$\leq 1.5 \times \text{ULN}$
	Amylase	$\leq 1.5 \times \text{ULN}$ and absence of clinical pancreatitis
Renal*	Serum creatinine	$\leq 1.5 \times \text{ULN}$
	CrCl by Cockcroft and Gault method: $\text{CrCl (mL/min)} = \frac{(140 - \text{age [years]}) \times \text{weight (kg)} \times (F)}{(72 \times \text{serum creatinine mg/dL})}$ ^a where F = 0.85 for females and F = 1 for males	$\geq 50 \text{ mL/min}$

*For patients with below ideal body weight, the 24-hour urine test may be used: ideal body weight (kg) = constant + 0.91 (height [cm] - 152.4); constant is 50 for men and 45.5 for women.

ALT, alanine transaminase; AST, aspartate transaminase; CrCl, creatinine clearance; INR, international normalised ratio; ULN, upper limit normal.

- 11 Adequate cardiac function as demonstrated by left ventricular ejection fraction (LVEF) $> 50\%$ on screening cardiac multigated acquisition (MUGA), magnetic resonance imaging (MRI), or echocardiogram (ECHO).

- 12 Willing and able to participate in all required study evaluations and procedures including receiving IV administration of study treatment and admission to the hospital, when required, for administration of study treatment and monitoring.
- 13 All patients must consent to and undergo both pretreatment and on-treatment fresh bone marrow aspirates and biopsies
- 14 For inclusion in the genetic component of the study, patients must fulfil the following additional criteria:
 - Provision of signed, written, and dated informed consent for genetic research. If a patient declines to participate in the genetic component of the study, there will be no penalty or loss of benefit to the patient. The patient will not be excluded from other aspects of the study described in this protocol, as long as they consented to the main study.

Reproduction

Women of childbearing potential must be willing to use highly effective contraceptive measures (see Section 5.3), should not be breastfeeding and must have a negative pregnancy test (serum) prior to start of dosing, or must have evidence of non-childbearing potential by fulfilling one of the following criteria at screening:

- 15 Women under 50 years of age would be considered postmenopausal if they have been amenorrhoeic for the last 12 months following the cessation of exogenous hormonal treatments and have serum follicle-stimulating hormone and luteinising hormone levels in the postmenopausal range for the institution.
- 16 Women with documentation of irreversible surgical sterilisation by hysterectomy, bilateral oophorectomy or bilateral salpingectomy but not tubal ligation.

Men should be willing to use barrier contraception (ie, condoms) and refrain from sperm donation during and after the conduct of the trial (see Section 5.3). If not done previously, storage of sperm before receiving AZD0466 will be advised to male patients with a desire to have children.

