For any other bleeding events eg, petechiae, purpura, bleeding gums, epistaxis, etc	Any	Monitor platelets and action as above if thrombocytopenia \geq Grade 3

^a Recovery of ANC to $\geq 0.5 \times 10^9/L$ only applicable for patients with ANC $\geq 0.5 \times 10^9/L$ at baseline/screening. For other patients discuss with Medical Monitor.

ANC, absolute neutrophil count.

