6.6.2 Retreatment Criteria

Administration of AZD0466 in subsequent cycles will be guided by presence of measurable disease and adequate haematopoiesis, as described below.

Criteria for holding administration of AZD0466

The haematological criteria for withholding AZD0466 are as follows (Table 6):

- 1 **Inadequate haematopoiesis** as demonstrated by lack of peripheral blood count recovery [absolute neutrophil count (ANC) $< 0.5 \times 10^9/L$, and platelet count $< 50 \times 10^9/L$] in the absence of active bone marrow leukaemia (marrow blasts $< 5\%$).
 - Some patients with low blood counts (ANC $< 0.5 \times 10^9/L$ and platelet count $< 50 \times 10^9/L$) may have an aplastic or hypoplastic marrow ($< 10\%$ cellularity on bone marrow core biopsy). In patients with an aplastic or hypoplastic marrow and high leukaemic burden (eg, 5% cellularity and 95% leukaemic blasts), or if the Investigator determines the hypocellularity is attributable to residual leukaemia and not AZD0466, continued administration of AZD0466 may be permitted after discussion with the Medical Monitor.
 - If AZD0466 is withheld due to cytopenias and bone marrow aplasia/hypoplasia ($< 10\%$ cellularity on core bone marrow core biopsy) in the absence of leukaemia (eg, 5% leukaemic blasts), the patient should be closely monitored for blood count recovery and a repeat bone marrow assessment should be considered at weekly intervals.
- 2 **Progressive disease** (Appendix J and Appendix K): permanently discontinue AZD0466 in the absence of clinical benefit after discussion with the Medical Monitor.

Criteria for administration/continuation of AZD0466

The next cycle of AZD0466 can proceed without delay if ANC $> 0.5 \times 10^9/L$ and platelets $> 50 \times 10^9/L$ (without platelet or growth factor support). For patients without peripheral blood count recovery, the next cycle can start if there is active leukaemia with 5% or higher blasts in the bone marrow.

Table 6 Treatment Criteria Based on Bone Marrow, ANC and Transfusion Independent Platelet Count in the Absence of Peripheral Blasts

Event	ANC ($10^9/L$)	Platelets ($10^9/L$)	Bone marrow	Action
Cycle 1	> 0.5	> 50	-	
 Evaluate bone marrow disease but continue to next cycle irrespective of percentage of blasts (unless determined to have rapidly progressive disease and taken off study)

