	< 0.5	< 50	< 5% blast and cellularity < 10%	
 No count recovery at day 35 hold AZD0466 wait to see if recovery at Day 42. If no recovery, repeat bone marrow at Day 42. Blasts count < 5% and no count recovery this is prolonged myelosuppression and a DLT. Discontinue AZD0466 Blasts count \geq 5% and no count recovery, either continue to Cycle 2 or discontinue due to lack of response after discussion with Medical Monitor
	< 0.5	< 50	> 5% blast	
 If significant reduction of leukaemic burden and clinical benefit as assessed by the Investigator, discuss with the Medical Monitor and may continue to Cycle 2. If lack of clinical response or benefit consider discontinuation from study.
Cycle 2 and beyond	> 0.5	> 50	< 5% blast and normal cellularity (> 10 %)	
 Continue to next cycle
			<5% blast and bone marrow hypocellular (< 10% cellularity)	
 Hold AZD0466 and monitor for count recovery and assess bone marrow weekly. Once adequate hemopoiesis met (> 20% cellularity) restart AZ0466. Consider restarting at one lower dose than the current dose.
	> 0.5	> 50	> 5% blast	
 Continue to next cycle if the patient is deriving benefit in the opinion of the Investigator
	< 0.5	< 50	Aplastic/ Hypoplastic (< 10% cellularity) and < 5% blasts	
 Hold and monitor for count recovery and assess bone marrow weekly. Once adequate hemopoiesis met (> 10% cellularity), restart AZ0466. Consider restarting at one lower dose than the current dose. If hypocellularity is due to high leukaemic burden (95% blast) or if Investigator attributes hypocellularity to residual leukaemia, consider dosing after discussion with Medical Monitor

Table 6 Treatment Criteria Based on Bone Marrow, ANC and Transfusion Independent Platelet Count in the Absence of Peripheral Blasts

Event	ANC ($10^9/L$)	Platelets ($10^9/L$)	Bone marrow	Action
	< 0.5	< 50	> 5% blast	
 Discuss with Medical Monitor consider discontinuation due to continued lack of response. Further cycles may be considered

ANC, absolute neutrophil count; DLT, dose-limiting toxicity.

Contact the Medical Monitor to discuss action with AZD0466 for any scenario not described above.

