Appendix O Prognostic Scoring for Myelodysplastic Syndrome

O 1 Prognostic Scoring System for MDS: The International Prognostic Scoring System – Revised (IPSS-R)

IPSS-R prognostic score values							
Prognostic variable	0	0.5	1.0	1.5	2.0	3.0	4.0
% Bone Marrow blasts	≤ 2	-	> 2–< 5	-	5–10	> 10	-
Cytogenetics	Very good	-	Good	-	Intermediate	Poor	Very Poor
Hemoglobin (g/dL)	≥ 10	-	8–< 10	< 8	-	-	-
Platelets ($\times 10^9/L$)	≥ 100	50– < 100	< 50	-	-	-	-
Neutrophils ($\times 10^9/L$)	≥ 0.8	< 0.8	-	-	-	-	-

IPSS-R prognostic risk categories	IPSS-R risk score
Very low	≤ 1.5
Low	> 1.5–3
Intermediate	> 3–4.5
High	> 4.5–6
Very high	> 6

O 2 MDS Cytogenetic Scoring System

MDS cytogenetic prognostic subgroups	Cytogenetic abnormalities
Very good	–Y, del(11q)
Good	Normal, del(5q), del(12p), del(20q), double including del(5q)
Intermediate	del(7q), +8, +19, i(17q), any other single or double independent clones
Poor	–7, inv(3)/t(3q)/del(3q), double including –7/del(7q), complex: 3 abnormalities
Very poor	Complex: > 3 abnormalities

O 3 References

Greenberg et al 2012

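### Criterion 6 admits MDS patients whose baseline already meets the Section 6.6.2 hold terms, and Table 6 and Section 11.4.7.2 disagree on when their unchanged cytopenia is a DLT

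*Protocol*

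**What the plan says.** **Entry.** Protocol Section 5.1 enrols "intermediate or higher risk myelodysplastic syndrome (MDS; Part A only"), the part in which DLTs guide escalation. For MDS, criterion 6 joins two conditions by and/or: more than 10% blasts, or "MDS with intermediate, high, or very high risk (risk score > 3) per the Revised International Prognosis Scoring System (IPSS-R"). The second is sufficient alone. Criterion 10 requires "Adequate organ function at screening defined in" Table 3, which lists hepatic, coagulation, pancreatic and renal limits but no neutrophil or platelet minimum.

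**Retreatment.** Section 6.6.2 withholds AZD0466 when ANC is below 0.5 and platelets are below 50 (both × 10⁹/L) "in the absence of active bone marrow leukaemia", which it defines as marrow blasts under 5%. Without count recovery, "the next cycle can start if there is active leukaemia with 5% or higher blasts in the bone marrow".

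**DLT.** For Cycle 1 with both counts low, blasts under 5% and cellularity under 10%, Table 6 holds treatment, repeats the marrow at Day 42 and then states: "Blasts count < 5% and no count recovery this is prolonged myelosuppression and a DLT". It orders discontinuation. Section 11.4.7.2 uses the same count and blast limits but sets marrow cellularity at under 5% by Day 42. It opens by excluding toxicity that is plainly a direct result of the malignancy.

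**Baseline.** Table 5 footnote a applies its ANC recovery test only to patients whose baseline ANC was at least 0.5, and adds: "For other patients discuss with Medical Monitor".

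**The concern.** The protocol uses two notions of active disease. For entry, MDS is active at an IPSS-R score above 3, whatever the blast count. For retreatment, disease is active only from 5% marrow blasts. A patient admitted under the first can fail the second on the day of enrolment, and the hold rule then reads an unchanged marrow as a failure to recover.

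Two things are at stake. Marrow failure present before treatment could be entered as drug toxicity in the DLT counts that feed the mTPI-2 recommendation. And whether these patients get beyond one cycle would rest on case-by-case decisions, which affects exposure, safety and response summaries by dose level.

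**Working it through.** The plan gives no figure to reproduce here. The check is an enumeration of Appendix O, followed by a walk through the rules.

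**Step 1: can such a patient enter?** Inputs are from the Appendix O table headed "IPSS-R prognostic score values". Platelets below 50 score 1.0. Neutrophils below 0.8, the band that contains ANC below 0.5, score 0.5. That leaves:

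- blasts *b*: 0 (up to 2%) or 1 (above 2% to below 5%)
- cytogenetics *c*: 0, 1, 2, 3 or 4
- haemoglobin *h*: 0, 1 or 1.5

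Score = *b* + *c* + *h* + 1.0 + 0.5. It exceeds 3 when *b* + *c* + *h* exceeds 1.5. There are 2 × 5 × 3 = 30 combinations. Those that fail are:

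- *b* = 0, *c* = 0: all three haemoglobin values (totals 1.5, 2.5, 3.0)
- *b* = 0, *c* = 1, *h* = 0 (total 2.5)
- *b* = 1, *c* = 0, *h* = 0 (total 2.5)

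That is 5 failures, so 30 − 5 = 25 qualify. Example: blasts up to 2% (0), good cytogenetics (1), haemoglobin 8 to below 10 g/dL (1), platelets below 50 (1), neutrophils below 0.8 (0.5): 0 + 1 + 1 + 1 + 0.5 = 3.5, intermediate risk, eligible.

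**Step 2: what happens if nothing changes in Cycle 1?** Take blasts under 5%, ANC under 0.5 and platelets under 50 at baseline and at the end of the cycle. The hold criterion in the Section 6.6.2 text is met; it carries no cellularity condition and no comparison with baseline. The count-recovery route (ANC above 0.5 and platelets above 50, unsupported) is closed, and so is the route through 5% blasts. Medical Monitor discussion remains.

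**Step 3: is it a DLT?** That depends on cellularity at Day 42, reading the Section 11.4.7.2 condition as marrow cellularity under 5%:

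| Cellularity | Table 6, Cycle 1 | Section 11.4.7.2 myelosuppression item |
|---|---|---|
| 10% or more | no matching row; Medical Monitor | not met |
| 5% to below 10% | DLT, discontinue | not met |
| below 5% | DLT, discontinue | met, unless excluded as malignancy-related |

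In the middle band the two passages disagree on whether a DLT occurred. In the last they can disagree, because Table 6 does not carry the malignancy exclusion. Neither compares counts with baseline, although the other-toxicity item in Section 11.4.7.2 does require worsening from baseline, and Table 5 footnote a has a baseline provision for ANC.

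**Step 4: what does one misattributed DLT do?** Read from Table 10:

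| Patients | Without it | With it |
|---|---|---|
| 3 | 0 DLTs: escalate | 1 DLT: stay |
| 3 | 1 DLT: stay | 2 DLTs: de-escalate |
| 5 | 1 DLT: escalate | 2 DLTs: de-escalate |

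**The case against.** The strongest reply is that the documents already say which DLT definition counts. Section 6.7 refers to Section 11.4.7, and SAP Section 4.14.2 defines DLTs by protocol Section 11.4.7.2, whose malignancy exclusion precedes every listed criterion. Unchanged marrow failure is the natural case for it. This largely stands for the analysis and would remove many such cases. It does not settle the matter at the site: the exclusion requires that the link to disease be clear and direct, which is a judgement, while Table 6 states the DLT and the discontinuation without qualification.

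Three stronger readings are tempting, and the documents do not support them.

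- A reader might infer that these patients are barred from Cycle 2. They are not. Section 6.6.2 allows dosing after Medical Monitor discussion when a hypocellular marrow is attributed to residual disease, and Table 6 refers unlisted scenarios to the Medical Monitor. The former is worded for leukaemia, however, so its reach to MDS is unclear.
- A reader might infer that any unchanged patient is scored a DLT. Both passages require a hypocellular marrow; at 10% cellularity or more neither applies.
- A reader might infer that the rules presuppose at least 5% blasts at entry. No passage says so. What can be shown is that they contain no MDS or baseline-count provision.

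Two further limits are fair. Table 10 guides the SRC, which also weighs the other safety, tolerability and PK data, so one DLT does not fix the decision. And SAP version 2.0 records that recruitment has stopped and that the MTD will not be estimated in this analysis.

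**Conclusion.** The concern holds in limited form. Criterion 6 and Section 6.6.2 conflict on what active disease means in MDS: an eligible, unchanged patient with blasts under 5% and both counts low meets a written hold rule, with no stated way forward except Medical Monitor discussion. Separately, Table 6 and Section 11.4.7.2 contradict each other on cellularity (below 10% against below 5%) and on the malignancy exclusion.

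The figure of 25 in 30 counts scoring combinations already restricted to severe cytopenia; it says nothing about how many patients are affected, which the documents do not give. The DLT risk is confined to hypocellular marrows, and under Section 11.4.7.2 to cases not attributed to the disease. The hold needs both counts low; a deficit in only one is not clearly covered. Where a misattribution does occur, a single case is enough to change the Table 10 recommendation in a cohort of 3 or 5.

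This should be corrected. With recruitment stopped, the protocol edits matter mainly if these rules are reused; the SAP still tabulates DLTs, so that part remains live.

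**What to change.** 1. Reconcile criterion 6, Section 6.6.2, Table 6 and Section 11.4.7.2 on three matters: what counts as active disease in MDS, how cytopenia already present at baseline is treated, and the cellularity threshold. What the reconciled rules say is a clinical matter for the sponsor.
2. State that one passage governs DLT scoring and have Table 6 refer to it. The SAP already relies on Section 11.4.7.2. Naming it does not settle which cellularity figure it should carry.
3. In the DLT table under SAP Section 4.14.2, flag patients whose baseline ANC, platelets and marrow blasts already met the count and blast terms of the myelosuppression item, so that a reader can see whether any reported DLT falls among them.

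The cost is wording in the protocol sections named and one derived flag in the SAP. Baseline counts and the screening marrow are already collected, so no new data are needed.
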